4 PLANNED ANALYSES

4.1 ANALYSES AND REPORTING

Study analyses for primary efficacy and safety endpoints will be conducted using Bayesian methods, consistent with other medical device submissions to CDRH to allow the computation of credible limits for assessment of the statistical hypotheses. This decision was made in advance of any data assessments for either efficacy or safety. Other outcomes, including secondary endpoints for which formal hypothesis testing is not prespecified, will be presented descriptively with Bayesian credible intervals to correspond to the primary or supportive analyses.

All analyses identified in this SAP relate to primary, secondary, and exploratory endpoints focused at time points, 30 days, 180 days, and up to and including 12 months. Key statistics and study results will be made available to the Project Team following database lock and prior to completion of the final CSR. Any post-hoc, exploratory analyses completed to support planned study analyses, which were not identified in this SAP, will be documented and reported in

appendices to the CSR. Any results from these unplanned analyses will also be clearly identified as post hoc in the text of the CSR.

Safety data will be reviewed and adjudication of all adverse events reported in the study will be performed by an independent blinded Clinical Events Committee (CEC); the CEC will also review all protocol deviations. Safety will be based on the CEC findings. In addition, a Data Safety and Monitoring Board (DSMB) will review all site-reported and CEC-adjudicated clinical data. These safety reviews will be conducted only for the benefit of members of the DSMB in accordance with the DSMB charter. Because these interim safety reviews will not include inference procedures (confidence intervals or hypothesis tests), and because these safety analyses reviews will not be shared outside the DSMB, no alpha spending adjustments are required for the final analyses.

4.2 INTERIM ANALYSES

No interim analyses are planned.

4.3 FINAL ANALYSES

Final statistical analyses will be performed as detailed below.

Two OPC sets will be considered in support of efficacy and safety as per the original protocol as well as more restrictive OPCs as follows:

- Primary: Original PG specified in the protocol (45% for efficacy and 25% for safety)
- Supportive: Updated PG presented to FDA at the Feb 2017 meeting (46% for efficacy and 15% for Safety).

Primary Analyses: The powers will be 80% to rule out a 45% OPC (efficacy) margin (lower bound) and 80% to rule out a 25% OPC (safety) margin (upper bound) using one-sided tests. The trial will be considered successful if the one-sided 95% credible lower bound of the efficacy rate exceeds the 45% OPC and the one-sided 95% credible upper bound of the safety rate is below the 25% OPC. The use of one-sided testing is consistent with the original protocol.

Supportive Analyses: The powers will be 90% to rule out a 46% OPC (efficacy) margin (lower bound) and 90% to rule out a 15% OPC (safety) margin (upper bound) using two-sided tests. The trial will be considered successful if the two-sided 95% credible lower bound of the efficacy rate exceeds the 46% OPC and the two-sided 95% credible upper bound of the safety rate is below the 15% OPC. The use of two-sided testing is consistent with the PIPELINE PMA and FDA guidance.

Study success is defined as achieving statistical significance for the primary OPCs.

Thus, both one-sided and two-sided credible intervals will be computed for the primary (one-sided) and supportive (two-sided) analyses. However, since the success standards are higher for both safety and efficacy for the supportive analyses than for the primary analyses, credible interval claims in support of labeling will be sought based on the more restrictive supportive analyses which are nested within the alternative hypotheses.

5 ANALYSIS POPULATIONS

The statistical analysis will use three populations:

- 1) The Intent to Treat (ITT) population will consist of all enrolled subjects who had an introduction of the FRED Implant System into the bloodstream. The ITT population will be used for all effectiveness analyses to test the efficacy hypothesis for both OPC sets.
- 2) The Safety Population will consist of all subjects in whom the investigational device was implanted as well as deaths due to technical failures during the index procedure. The Safety Population will be used to test the safety hypothesis for both OPC sets.
- 3) The Per Protocol Population will consist of all subjects in the ITT Population for whom there were no major protocol deviations. All protocol deviations will be assessed by the Clinical Events Committee.

The primary and secondary effectiveness endpoints will also be evaluated for the Per Protocol Population.

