Additionally, other safety endpoints will also be assessed based on Adverse Events. The number of subjects and the number of adverse events per subjects will be presented for Adverse Events, unanticipated Adverse Events, Serious Adverse Events, and unanticipated Serious Adverse Events. The results will be provided by system organ class and preferred term. Narrative case summaries will be provided for each Serious Adverse Event. Two-sided 95% credible intervals will be presented for each adverse event with ≥5% incidence.

Technical Failures

Technical failure subjects will be presented separately but will be excluded from the ITT and Per Protocol populations if they did not receive the device. They will be included in the Safety population.

A FRED procedure will be categorized as a technical failure if the following occurs:

- Failed FRED Device Deployment Due to Technical Issues with the FRED Device
 - If the FRED Device enters the blood stream and cannot be deployed secondary to technical issues with the device itself (e.g., FRED Device malfunction or failure to access the target site due to the FRED Device), the Subject will be counted as enrolled with intent-to-treat. This will be considered as a secondary endpoint failure. The Subject will be maintained within the study and will not be replaced by another Subject. The Subject will be monitored for any Adverse Event for one (1) week

following the failed deployment due to a technical issue related to the FRED Device. Unless medically necessary to pursue treatment sooner, it is recommended that further attempts to treat the target aneurysm be deferred for a minimum of one (1) week so that any potential procedural Adverse Events may be monitored.

- Failed Device Deployment Due to Issues Related to the Procedure

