 - If the FRED Device cannot be deployed due to any other issues related to the procedure, the Subject will be counted as enrolled but not treated and will not be considered a secondary endpoint failure. The Subject will be maintained within the study for one (1) week. Thereafter, the Subject may be replaced in the study. The Subject will be monitored for any Adverse Event for one (1) week following the failed deployment due to issues related to the procedure. If the Subject has an Adverse Event, that Subject will also have 30-day, 6-month and 12-month clinical follow-ups. An angiographic follow-up will not be required unless the clinician believes it is medically necessary. Unless medically necessary to pursue treatment sooner, it is recommended that further attempts to treat the target aneurysm be deferred for a minimum of one (1) week so that any potential procedural Adverse Events may be monitored.

Subgroup Analysis

Results for the primary and secondary endpoints will be stratified by the following subgroups:

- Location (anterior, posterior)
- Age (<55, 55-64, ≥65)
- Gender: results will be stratified by gender
- Anatomic location (zone 1, 2 and 3)
- Region (Japan, other countries)

Since it is not possible to determine any observed differences are truly due to a difference in treatment effect, any observed significant differences in outcomes ($p < 0.1$) across subgroups will be examined and compared to available literature regarding known risk effects for the subgroups.

Missing Data

In general, all analyses will be performed using the ITT analysis set, which constitutes all available cases and all available visits. Every effort will be made to get 12 month follow-up for all study patients. The primary endpoints will be analyzed first without imputing missing or incomplete data. Multiple sensitivity analyses will be performed in order to better understand the potential effect of missing or incomplete data on the conclusions for the primary endpoints. These sensitivity analyses will impute values for subjects who are event free (for the specific primary endpoint), but do not have complete data. The analysis method used on the imputed datasets will use the binary result (i.e. simple event percents).

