2 PROSPECTIVE STUDY OVERVIEW

FRED is a single-arm pivotal study in the treatment of intracranial aneurysms in which subjects will be implanted with FRED. Current common therapies, such as surgical or endovascular approaches, are not able to treat intracranial aneurysms with wide necks effectively. Currently in the US, there is one flow diverter, the Pipeline Embolization Device (PED), approved by FDA and there are currently three CE Mark approvals for Pipeline, SILK and the NeuroEndoGraft.

Subjects enrolled into the study and treated with FRED shall be followed at discharge and 30 days, 180 days and 12 months. A subject considered enrolled but not treated because of a failed FRED deployment because of issues related to the procedure shall be closely monitored for one (1) week. If the device entered the blood stream and the subject has an Adverse Event, that subject will have the 30-day, 180 days and 12-month clinical follow-ups. If the FRED Device enters the blood stream and cannot be deployed secondary to technical issues with the device itself (e.g., FRED Device malfunction or failure to access the target site due to the FRED Device), the Subject will be counted as enrolled with intent-to-treat. This will be considered as a secondary endpoint failure. The Subject will be maintained within the study and will not be replaced by another Subject. If the FRED device never entered the subject's bloodstream that subject will be excluded from all the analysis populations. No additional analysis is planned for data collected beyond 12 months study follow up period.

This study incorporates the use of an independent blinded Clinical Events Committee (CEC) which reviewed and adjudicated all the primary and secondary safety outcome measures of the study, as well as all the adverse events and technical events reported in the study. In addition, independent blinded Data Safety and Monitoring Board which provided study safety and efficacy oversight reviewed all the site-reported and CEC adjudicated clinical data of the FRED study, and an independent angiographic core laboratory determined aneurysm occlusion and the degree of device stenosis reported by the investigational sites.

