3.2 PRIMARY ENDPOINTS

Primary Safety Endpoint:

The primary safety endpoint is the proportion of subjects who experience one or more of the following:

- a. death or major stroke within 30 days post procedure
 - b. neurological death or major ipsilateral stroke within 12 months post procedure
- ✦ *A major stroke is defined as a new neurological event that persists for > 24 hours and results in a ≥ 4 -point increase in the NIHSS score compared to baseline or compared to any subsequent lower score.*
 - ✦ *A major ipsilateral stroke is defined as that occurring within the vascular distribution of the stented artery*
 - ✦ *Neurologic death is defined as a death which has been adjudicated by the independent clinical events committee to have directly resulted from a neurologic cause*

Primary Effectiveness Endpoint:

Proportion of subjects with complete occlusion of the target aneurysm utilizing the Raymond Scale and $\leq 50\%$ stenosis of the parent artery at the target IA at 12 months as assessed by angiography and in whom an alternative treatment of the target IA had not been performed within 12 months post-FRED placement; where an alternative treatment is defined as re-treatment of the target aneurysm with an alternative treatment modality including open repair, endovascular placement of an additional stent or treatment of In-stent Stenosis observed at the 180 day or 12 month follow-up time-points or at an unscheduled study follow up visit.

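### The primary safety test omits survivors in whom FRED was introduced but not implanted, the protocol contradicts itself on this, and the efficacy scoring of such subjects is left open

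*SAP*

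**What the plan says.** **Safety set.** SAP section 5 and protocol 6.1 both define the Safety Population as "all subjects in whom the investigational device was implanted as well as deaths due to technical failures during the index procedure" and use it for the safety hypothesis. Under SAP 3.2 the endpoint counts "death or major stroke within 30 days post procedure", plus neurological death or major ipsilateral stroke within 12 months. Ipsilateral is tied to a stent: "A major ipsilateral stroke is defined as that occurring within the vascular distribution of the stented artery".

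**Technical failures.** Protocol 6.2 (Technical Failures) says of these subjects "They will be included in the Safety population", with no limit to deaths. It also says they "will be excluded from the ITT and Per Protocol populations if they did not receive the device". Its second category begins "If the FRED Device cannot be deployed due to any other issues related to the procedure" and does not require the device to have entered the bloodstream. SAP section 2 says that where the device never entered the "bloodstream that subject will be excluded from all the analysis populations".

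**Efficacy set.** The SAP's ITT population needs only introduction into the bloodstream. Protocol 6.1 adds 12 months of follow-up or earlier failure. SAP 7.1 describes the endpoint as a percentage of the ITT population, but its posterior uses a count of evaluable subjects that is not defined. Of a device-related failed deployment, protocol 6.2 and SAP section 2 say only: "This will be considered as a secondary endpoint failure".

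**Counts.** SAP section 1 gives 145 subjects, with ITT identical to Safety. SAP 7.2 gives 140 enrolled and treated.

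**The concern.** Membership of the safety set depends on the outcome. Among non-implanted subjects, a death from a technical failure at the index procedure enters the numerator and denominator, while a survivor with a disabling procedural stroke enters neither. That stroke is an outcome the co-primary test exists to count. It would not be hidden, because technical failures are presented separately and all adverse events are adjudicated (SAP 4.1), but it would not bear on the success decision.

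Two analysts, one following SAP section 5 and the other the protocol's Technical Failures text, would use different safety denominators. Two readings of evaluable likewise give different efficacy denominators. Dropping subjects who cannot be successes can only favour the device on efficacy. On safety, the omission favours the device only if omitted subjects have a higher event rate than implanted ones.

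**Working it through.** **1. The texts side by side, for a survivor with FRED introduced but not implanted**

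| Source | Safety | ITT |
|---|---|---|
| SAP 5 | Out | In |
| Protocol 6.1 | Out | In, if followed 12 months or failed earlier |
| Protocol 6.2, Technical Failures | In | Out if the device was not received (term undefined) |

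The ITT entries in the first and third rows agree only if receiving the device means bloodstream entry, which is not stated. The third row's Safety entry is also too wide, since it can take in subjects without bloodstream entry, whom SAP section 2 removes from every population.

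**2. Can such a subject be dropped from efficacy?** Four provisions allow it. The non-occlusion limb of the protocol 6.2 failure list presupposes a deployed, properly positioned device. Protocol 11.6 gives a failed deployment without an adverse event no later visits. SAP 6.6 does not impute primary effectiveness for subjects without follow-up data. SAP 7.1 leaves evaluable undefined.

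**3. Decision rule.** Inputs from SAP 7.1 and 7.2: Beta(1,1) prior, goals 0.45 and 0.25, success if the posterior probability exceeds 0.95. As calibration, exact binomial tests at N = 140 give power of 90.6%, 90.2%, 90.1% and 92.1%, against 90, 90, 90 and 92 in the SAP 7.2 table.

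**4. Efficacy type I error.** Assume 145 introduced subjects with a true success rate of 45% across all of them. If k certain non-successes are dropped, n = 145 − k and the success rate among the rest is 0.45 × 145 / n. Type I error is P(X ≥ cut-off).

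| k (assumed) | n | Cut-off | Rate in n | Type I error | Same cut-off, rate held at 0.45 |
|---|---|---|---|---|---|
| 0 | 145 | 76 | 0.4500 | 4.4% | 4.4% |
| 1 | 144 | 75 | 0.4531 | 6.1% | 5.2% |
| 3 | 142 | 74 | 0.4595 | 8.3% | 5.3% |
| 5 | 140 | 73 | 0.4661 | 11.0% | 5.4% |

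The last column isolates the change in n. About half of the rise at k = 1 is discreteness.

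**5. Safety type I error.** The true event rate over all 145 is 25%, or 36.25 expected events. If k subjects with event rate r are omitted, the rate among the rest is (36.25 − k·r)/n. Type I error is P(X ≤ maximum events).

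| k (assumed) | n | Max events | r = 0 | r = 0.25 | r = 1 |
|---|---|---|---|---|---|
| 0 | 145 | 27 | 4.3% | 4.3% | 4.3% |
| 1 | 144 | 27 | 4.3% | 4.8% | 6.4% |
| 3 | 142 | 26 | 2.7% | 3.7% | 8.8% |
| 5 | 140 | 26 | 2.7% | 4.5% | 16.8% |

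The r = 1 column is an extreme.

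**6. Boundary cases.** With s events in n, P(π < 0.25) comes from Beta(1 + s, 1 + n − s). It is 0.957 for 27/144 (pass). Adding one survivor with a stroke gives 28/145, 0.940 (fail). Adding one event-free survivor gives 27/145, 0.961 (pass). On efficacy, 73/140 gives 0.955 (pass) and 73/145 gives 0.903 (fail).

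**7. At the SAP's own alternatives.** At N = 140, 0.58 × 140 is about 81 successes and 0.15 × 140 = 21 events. Adding five adverse subjects gives 81/145 (0.996) and 26/145 (0.975). Both primary tests still pass.

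**The case against.** The best counter-argument is that nothing happens in this dataset. If ITT and Safety are identical at 145, the SAP's definitions imply no surviving introduced-only subject, and protocol 13.4 requires another device to be available. No document supports k as high as 5, the 16.8% figure needs all five to have events, and study success needs both endpoints. This stands as a limit on the size. It does not settle k, because 145 and 140 are unreconciled; equally, that gap is not evidence of failed deployments.

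On efficacy, the SAP summary frames success as treatment with the FRED device, SAP 7.1 refers to the ITT population, and device-related failures are kept in the study without replacement. The more natural reading is therefore non-success. A subject later retreated may fail under the alternative-treatment limb, and SAP 7.3 plans tipping-point analyses. These points narrow the gap mainly to subjects without recorded retreatment. They do not close it, because the tipping-point analyses address missing endpoints and do not set the primary score.

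The type I error figures also assume that the goals apply to all subjects with the device introduced. The documents do not say whether the literature denominators were built that way.

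**Conclusion.** The concern holds and should be fixed. The safety definition is outcome-dependent and is contradicted by current protocol text, within the protocol as well as between the protocol and the SAP. The efficacy score for introduced-only subjects is open, although the text leans towards non-success.

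The size rests on an unknown k. If k is 0, nothing changes. For assumed k of 1 to 5, with the true rate at the goal, efficacy type I error would be 6.1% to 11.0% if the subjects are dropped. Safety type I error would range from 2.7% to 16.8% depending on their event rate. A single subject changes the conclusion only at the boundary, and at the SAP's planning alternatives even five adverse subjects change neither primary result.

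**What to change.** - In SAP 5 and protocol 6.1, define the Safety Population as all subjects in whom FRED entered the bloodstream, counting every primary safety event whether or not the device was implanted. This reuses the SAP's own ITT criterion.
- In SAP 3.2 and the matching protocol text, define ipsilateral by the target artery when no stent was placed.
- Limit both population sentences in the protocol's Technical Failures text to match: with bloodstream entry, in Safety and ITT; without it, in neither.
- Align the protocol 6.1 ITT definition with SAP 5.
- State in SAP 7.1 that an ITT subject without a successfully deployed FRED is a primary efficacy non-success and stays in n. Define evaluable in SAP 7.1 and 7.2.
- Report the number of introduced-but-not-implanted subjects, and reconcile 145 with 140.
- Protocol 6.2, protocol 11.6 and SAP section 2 state different conditions for following failed deployments and must be reconciled.

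The cost is SAP and protocol wording only. If k is 0, no result changes. If k is above 0, efficacy can only become less favourable than under dropping, while safety may move in either direction.

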6 GENERAL CONSIDERATIONS

6.1 BASELINE

Unless otherwise specified, baseline is defined as the last non-missing measurement taken prior to or on the study start date/time.

6.2 CRITERIA FOR SUCCESS FOR PRIMARY ENDPOINT ANALYSES

Primary efficacy and safety will be assessed by employing a Bayesian approach. Bayesian statistics are a principled approach for learning from evidence as it accumulates (FDA 2010, FDA guidance for industry and FDA staff guidance for the use of Bayesian statistics in medical device clinical trials, FDA CDRH CBER, February 5, 2010).

For the primary endpoints, the criterion for success is based on the posterior probability of the alternative hypothesis. The FRED device will be declared efficacious if the one-sided 95% lower

credible limit is at least 45%. The performance goal was obtained from a formal comprehensive literature review and meta-analysis of results from studies of flow diverters to treat patients matched to the FRED study subjects during the first year after treatment. Similarly, the FRED will be declared safe if the one-sided 95% upper credible limit is at most 25%. The performance goal used in the P100018 SSED of the Pipeline PUFs study was 20%.

However, the definition used in the PUFs study did not include all death and major stroke within 30 days, only death of neurologic cause and major ipsilateral strokes, and it was only evaluated through 180 days, not 12 months. For this reason, the performance goal utilized here is slightly higher. The primary safety endpoint in this study has not been used or reported as such previously, so the magnitude of the effect of this change is unknown. For the purposes of the current study a conservative 5% adjustment is used, resulting in a 25% performance goal (20% from above + 5% conservative adjustment).

6.3 ANALYSIS SOFTWARE

Statistical analyses will be performed using SAS version 9.3 or above (SAS Institute, Cary, NC, USA), R version 3.2 or above (R Foundation for Statistical Computing, Vienna, Austria) or other widely accepted statistical software. For Bayesian analyses of the primary endpoints, posterior estimates of modeled parameters will be reported along with the relevant one-sided and two-sided 95% credible intervals.

Descriptive statistics for continuous variables will include the mean, standard deviation, median, quartiles, and sample size for each treatment group. Categorical variables will be summarized using frequency distributions including counts and percentages. Proportions will be calculated using known non-missing values.

